# 7.7. Concomitant Medications

Concomitant medications will be assigned an 11-digit code using the World Health Organization Drug Dictionary (WHO DD) drug codes. Concomitant medications will be further coded to the appropriate Anatomical-Therapeutic-Chemical (ATC) code indicating therapeutic classification. A tabular summary of concomitant medications by drug class will be presented for the Safety Population.

# 7.8. Efficacy Analysis

The efficacy analysis will be based on the safety population. Each efficacy endpoint will be listed and summarized descriptively by group of the optimized dose, if applicable. In addition, if applicable, subjects who received adjunctive stimulant therapy will be identified by flagging for categorical summary. Total and subscale scores/points for AISRS, CGI-S, CGI-I, GAD-7, BRIEF-A, SDQ, and AAQoL will be summarized by optimized dose (if applicable) and visit and will be examined. Baseline will be defined for all subjects as the last non-missing value prior to SPN-812 dosing in Study 812P311.

### 7.9. Safety Analysis

Safety analyses will be performed by optimized dose group and overall based on the Safety Population.

The incidence rate of AEs will be calculated for each system organ class (SOC) and preferred term (PT). The severity of the AEs and the relationship to SM will be summarized for each SOC and PT.

AEs will be summarized using discrete summaries at the subject and event level by SOC and PT, and by severity and relationship separately. Verbatim description and Medical Dictionary for Regulatory Activities (MedDRA) SOCs and PTs for all AEs will be contained in the subject data listings.

Clinical laboratory values will be summarized by visit by optimized dose group and overall using descriptive statistics. For quantitative laboratory parameters, both actual values and change from baseline values will be summarized.

Vital signs will be summarized by visit by optimized dose group and overall using descriptive statistics. Both actual values and change from baseline will be summarized.

ECG results will be summarized by visit by optimized dose group and overall using descriptive statistics (for quantitative ECG parameters) and frequency tables (for qualitative ECG parameters, including the overall ECG finding).

C-SSRS outcomes will be summarized using number and percent of subjects by categories for suicidal ideation only, suicidal behavior only and suicidality (ideation and behavior combined). The summary will be presented by optimized dose group and overall.

# 7.10. Sample Size and Power Considerations

There is no consideration for power or sample size determination in this open label study. The present study is an extension of the blinded 812P306 study in patients with ADHD.

## 8. DOCUMENTATION

#### 8.1. Adherence to the Protocol

The Investigator agrees, when signing the protocol, to adhere to the instructions and procedures described within and to the principles of ICH GCP as well as all governing local regulations and principles for medical research.

The protocol, ICF, and appropriate related documents must be reviewed and approved by an IRB constituted and functioning in accordance with ICH E6 and any local regulations. Documentation of IRB compliance with the ICH and any local regulations regarding constitution and review conduct will be provided to the Sponsor.

A signed letter of study approval from the IRB must be sent to the Investigator with a copy to the Sponsor prior to study start and the release of SM to the site by the Sponsor or its designee. If the IRB decides to suspend or terminate the study, the Investigator will immediately send the notice of study suspension or termination by the IRB to the Sponsor.

### 8.2. Changes to the Protocol

Changes to the protocol will not be made without written approval from the Sponsor.

Any change to the protocol requires a written protocol amendment or administrative change that must be approved by the Sponsor before implementation. Amendments specifically affecting the safety of subjects, the scope of the investigation, or the scientific quality of the study require additional approval by the applicable IRB, and in some cases, filings to the regulatory authority. These requirements should in no way prevent any immediate action from being taken by the Investigator, or by the Sponsor, in the interest of preserving the safety of all subjects included in the study. If an immediate change to the protocol is felt by the Investigator to be necessary for safety reasons, the Medical Monitor, and IRB must be notified promptly.

Changes to the protocol which are administrative in nature do not require formal protocol amendments or IRB approval, but the IRB must be kept informed of such changes. In these cases, the Sponsor or CRO will send a letter to the IRB detailing such changes.

### 8.3. Data Quality Assurance

This study will be organized, performed, and reported in compliance with the protocol, standard operating procedures (SOPs), working practice documents, and applicable regulations and guidelines. Site visit audits may be made periodically by the Sponsor's Quality Assurance team or qualified designee, which is an independent function from the study conduct team.

### 8.3.1. Data Collection

The primary source document will be the subject's medical record. If separate research records are maintained by the Investigator(s), both the medical record and the research

record will be considered the source documents for the purposes of monitoring and auditing the study.

Electronic data collection techniques will be used to collect data directly from the study sites using eCRFs. The electronic data will be stored centrally in a fully validated clinical database.

Data recorded on source documents will be transcribed into the eCRFs in accordance with the eCRF Completion Instructions that are provided to the study sites. The Investigator is responsible for ensuring that all sections of each eCRF are completed correctly, and that entries can be verified against source documents. The eCRFs will be monitored for completeness and accuracy against the source documents by the CRA(s) on a regular basis. Inconsistencies between the eCRFs and source documents will be resolved in accordance with the principles of GCP.

# 8.3.2. Clinical Data Management

Data from eCRFs and other external data (e.g., laboratory data) will be entered into or merged with a clinical database as specified in the data management plan. Quality control and data validation procedures will be applied to ensure the validity and accuracy of the clinical database.

# 8.3.3. Database Quality Assurance

In accordance with the vendor's procedures, the clinical database will be reviewed and checked for omissions, apparent errors, and values requiring further clarification using computerized and manual procedures. Data queries requiring clarification will be documented and returned to the study site for resolution. Only authorized personnel will make corrections to the clinical database, and all corrections will be documented in an audit trail.

# 8.4. Retention of Records

The Investigator has the responsibility to retain all study "essential documents", as described in ICH E6 for at least two years after approval of a marketing application or after formal discontinuation of the clinical program. Essential documents include but not limited to the protocol, eCRFs, source documents, laboratory test results, SM inventory records, Investigator's Brochure, regulatory agency registration documents (e.g., FDA form 1572, ICFs, and IRB correspondence). The Investigator must obtain written permission from Supernus prior to the destruction of any study document.

# 8.5. Auditing Procedures

In addition to the routine monitoring procedures, the Sponsor's Corporate Quality Assurance department or qualified designee may conduct audits of clinical research activities in accordance with the Sponsor's written SOPs to evaluate compliance with the principles of ICH GCP and all applicable local regulations. A government regulatory authority may also wish to conduct an inspection (during the study or after its completion). If an inspection is requested by a regulatory authority, the Investigator must inform the Sponsor and the CRO immediately that this request has been made. These records must be made available at reasonable times for inspection and duplication, if required, by a properly authorized representative of the US FDA in accordance with the US 21 Code of Federal Regulation (CFR) 312.68 or other national or foreign regulatory authorities in accordance with regulatory requirements.

### 8.6. Publication of Results

Any presentation or publication of data collected as a direct or indirect result of this trial will be considered as a joint publication by the Investigator(s) and the appropriate personnel at the Sponsor's site. Authorship will be determined by mutual agreement. All manuscripts, abstracts or other modes of presentation arising from the results of the study must be reviewed and approved in writing by the Sponsor, prior to submission for publication or presentation. No publication or presentation with respect to the study shall be made until all Sponsor comments on the proposed publication or presentation have been addressed to the Sponsor's satisfaction.

The detailed obligations regarding the publication of any data, material results, or other information, generated or created in relation to the study shall be outlined in the agreement between each Investigator and the Sponsor or designee.

### 8.7. Financing and Insurance

Financing and Insurance information will be set forth in a separate document between the Investigator and Sponsor (provided by the Sponsor or designee).

### 8.8. Disclosure and Confidentiality

The contents of this protocol, any amendments, and results obtained during the course of this study will be kept confidential by the Investigator, the Investigator's staff, and the IRB and will not be disclosed in whole or in part to others or used for any purpose other than reviewing or performing the study without the written consent of the Sponsor. No data collected as part of this study will appear in any written work, including publications, without the written consent of Sponsor.

All persons assisting in the performance of this study must be bound by the obligations of confidentiality and non-use set forth in the Confidentiality Agreement between the Investigator and Sponsor.

### 8.9. Discontinuation of Study

The Sponsor reserves the right to discontinue the study for medical or administrative reasons at any time. The Investigator will be reimbursed for reasonable expenses covering subjects, use of live-in facilities, laboratory tests, and other professional fees. The Investigator will refund the excess of payments made in advance.

The Investigator reserves the right to discontinue the study should his/her judgment so dictate. The Investigator will notify the IRB in case of study discontinuation. Study records must be retained as noted above.

# 9. ETHICS

### 9.1. Institutional Review Boards

The IRB that approved this study and the approval letters will be included in the clinical study report for this protocol.

The protocol, any protocol amendments, and the ICF will be reviewed and approved by the appropriate IRB before subjects are enrolled. The Investigators or Sponsor will submit, depending on local regulations, periodic reports and inform the IRB of any reportable AEs per ICH guidelines and local IRB standards of practice.

# 9.2. Ethical Conduct of the Study

This study will be conducted in accordance with SOPs from both the Sponsor and the CRO. These SOPs are designed to ensure adherence to GCP guidelines as required by:

- Declaration of Helsinki, 1964 ("Recommendations Guiding Physicians in Biomedical Research Involving Human Patients"), and all its accepted amendments to date concerning medical research in humans.
- ICH Guideline for GCP (Committee for Proprietary Medicinal Products/ICH/135/95) of the European Agency for the Evaluation of Medicinal Products, Committee for Proprietary Medicinal Products, ICH of Pharmaceuticals for Human Use.
- United States (US) CFR dealing with clinical studies (21 CFR, including parts 50 and 56 concerning Patient Informed Consent/Assent and IRB regulations).
- Local, national legal guidelines.

### 9.3. Investigators and Study Personnel

This study will be conducted by qualified Investigators under the sponsorship of Supernus Pharmaceuticals, Inc. (Sponsor).

Contact persons at the Sponsor and the CROs are listed in the reference binder provided to each investigational site. The study will be monitored by qualified personnel from the Sponsor or their designees, such as the CROs, for their respective sites. Medical writing, data management, and statistical analyses will be performed by the CROs. Laboratory tests will be conducted by a central laboratory as designated in the reference binder.

### 9.4. Subject Information and Consent

The Investigator (or designee) will inform the subject of all aspects pertaining to the subject's participation in the study and will provide oral and written information describing the nature and duration of the study, the procedures involved, the expected duration, the potential risks and benefits involved, and any potential discomfort.

The process for obtaining informed consent will be in accordance with all applicable regulatory requirements. The Investigator (or designee) and subject must sign and date the ICF before the subject can participate in the study. The subject will be given a copy

of the signed and dated ICF and the original will be retained in the investigational site study records.

The decision regarding subject participation in the study is entirely voluntary. The Investigator (or designee) must emphasize to the subject that consent, regarding study participation, may be withdrawn at any time without penalty or loss of benefits to which the subject is otherwise entitled.

If the ICF is amended during the study, the Investigator must follow all applicable regulatory requirements pertaining to approval of the amended ICF by the IRB and use the amended ICF (including ongoing subjects).

5.2	List of Listings
5.3	List of Figures
6	REFERENCES

ABBREVIATIONS

Abbreviation	Definition
AAQoL	Adult ADHD Quality of Life
ADHD	Attention-Deficit/Hyperactivity Disorder
AE	adverse event
AESI	adverse events of special interest
AISRS	ADHD Investigator Symptom Rating Scale
ALP	alkaline phosphatase
ALT	alanine aminotransferase
AST	aspartate aminotransferase
ATC	Anatomical Therapeutic Chemical
BMI	body mass index
BRIEF-A	Behavior Rating Inventory of Executive Function – Adult Version
BUN	blood urea nitrogen
CBC	complete blood count
CFB	change from baseline
CGI-I	Clinical Global Impressions Scale – Improvement
CGI-S	Clinical Global Impressions Scale – Severity of Illness
CRO	contract research organization
C-SSRS	Columbia-Suicide Severity Rating Scale
ECG	electrocardiogram
EOS	end of study
ER	extended-release
FSH	follicle stimulating hormone
GAD	generalized anxiety disorder
HCT	hematocrit
LLT	lower level term
mmol/L	millimoles per liter
msec	millisecond
MedDRA	Medical Dictionary for Regulatory Affairs

Abbreviation	Definition
N/A	not available
OLE	open-label extension
PCS	potentially clinically significant
PE	physical examination
PN	preferred name
PT	preferred term
QTcF	QT interval corrected for heart rate using Fridericia's correction formula
RBC	red blood cell
SAE	serious adverse event
SAP	statistical analysis plan
SD	standard deviation
SDQ	Symptoms of Depression Questionnaire
SI	International System of Units
SOC	system organ class
TEAE	treatment-emergent adverse event
ULN	upper limit of normal
WBC	white blood cells

1 INTRODUCTION

Study 812P311 is an open-label extension (OLE), long-term, multicenter, flexible-dose study of SPN-812 in adults diagnosed with Attention-Deficit/Hyperactivity Disorder (ADHD). Up to 366 subjects will be enrolled. Subjects who have completed Study 812P306 (a randomized, double-blind, placebo-controlled study of SPN-812 for the treatment of ADHD) will be eligible for enrollment into Study 812P311. Interest and suitability will be ascertained at the last 1 to 2 visits of 812P306 to allow immediate enrollment into Study 812P311 for subjects who complete Study 812P306

2 DATA CONVENTIONS FOR ANALYSIS

The Safety Population is defined as all subjects who are enrolled and receive at least one dose of SPN-812 during the OLE study.

Safety will be assessed from data based on the analysis of adverse events (AE), potentially clinically significant (PCS) laboratory evaluations, abnormal liver enzymes and liver function tests, abnormal vital signs, electrocardiogram (ECG) results, Columbia Suicide Severity Rating Scale (C-SSRS) and caffeine intake. Subject disposition (including reasons for premature terminations), subject demographics, physical assessment, and exposure to study drug will also be presented.

2.1 Disposition of Subjects and Withdrawals

Subject disposition summary will be presented for the Safety Population. Disposition will include tabulations of the number and percentage of subjects in each of the following categories:

- Subjects dosed
- Subjects completed study
- Subjects early discontinued

The primary reason for early discontinuation will be summarized. The reason for early discontinuation may include any of the following:

- Adverse event
- Death
- Lost to follow-up
- Non-compliance with study drug
- Withdrawal of consent by subject
- Lack of efficacy
- Investigator's decision
- Misuse or abuse of study drug

Supernus Pharmaceuticals, Inc.

CONFIDENTIAL

- Study terminated by sponsor
- Other

2.2 **Protocol Deviations**

A protocol deviation is defined as any change, divergence, or departure from the study design or procedures defined in the protocol. Protocol deviations will be listed and summarized.

2.3 Demographic Characteristics

Demographic characteristics include:

- Age (18-44, 45-65)
- Sex (male, female)
- Race
- Ethnicity (Hispanic, Non-Hispanic)
- Height
- Weight
- Body mass index (BMI)

The number and percent of subjects reporting various medical histories, grouped by Medical Dictionary of Regulatory Activities (MedDRA) system organ class (SOC) and preferred term (PT) will be analyzed. Medical history will be coded using MedDRA Version 22.1 This analysis will be conducted for the Safety Population.

Alcohol, tobacco, and substance use collected at screening will be listed. Subject training module data will also be listed.

2.4 Study Drug Exposure

Study drug exposure is collected as both actual and planned dose and duration of exposure to SPN-812.

2.5 Efficacy Data

 The adult ADHD Investigator Symptom Rating Scale (AISRS) was developed to better measure the presence and severity of ADHD symptoms based on DSM-IV diagnostic criteria in adult subjects⁷. It is a semi-structured clinical interview with suggested prompts for each item to improve inter-rater reliability. The scale consists of 18 items that directly correspond to the 18 symptoms of ADHD and are further subdivided into 2 subscales: Inattention (9 items) and Hyperactivity/Impulsivity (9 items). During the interview with the subject, the clinician/investigator rates the frequency and severity of each symptom on a 4-point Likert-type scale, where 0 = None, 1 = Mild, 2 = Moderate,

Supernus Pharmaceuticals, Inc.

CONFIDENTIAL

and 3 = Severe, with a maximum total score of 54 points and maximum subscale scores of 27 points each.

- 2) The Clinical Global Impressions scale was developed to provide a brief, stand-alone assessment of the clinician's view of a subject's global functioning prior to and after the administration of SPN-812. The Clinical Global Impression Severity of Illness (CGI-S) is a single item clinician rating of clinician's assessment of the severity of the ADHD symptoms in relation to the clinician's total experience with subjects with ADHD. The Clinical Global Impression Improvement Scale (CGI-I) is an assessment of how much the subject's illness has improved or worsened relative to a baseline state prior to treatment. Both CGI-S and CGI-I are rated on a 7-point scale of 1 to 7 with 7 being "extremely ill" or "very much worse", respectively. Successful therapy is indicated by a lower overall score in subsequent testing.
- 3) The CGI-S is evaluated on a 7-point scale with 1 = Normal/not at all ill, 2 = Borderline Ill, 3 = Mildly Ill, 4 = Moderately Ill, 5 = Markedly Ill, 6 = Severely Ill, and 7 = Extremely Ill.
- 4) CGI-I, relative to the condition at baseline, will be evaluated by the investigator at each post-baseline visit on a 7-point scale with 1 = Very much improved, 2 = Much improved, 3 = Minimally improved, 4 = No change, 5 = Minimally worse, 6 = Much worse, and 7 = Very much worse.
- 5) Generalized Anxiety Disorder 7 scale (GAD-7) is a self-reported 7-item questionnaire for screening and measuring the severity of generalized anxiety disorder⁹. The GAD-7 measures the severity of various symptoms of generalized anxiety disorder over the past 2 weeks according to reported response categories with assigned points. The subject scores each GAD-7 item on 4-point Likert scale, where 0 = Not at all, 1 = Several days, 2 = More than half the days, and 3 = Nearly every day. GAD-7 total scores range from 0 to 21, where a total score of 1 to 4 = None/Minimal anxiety, 5 to 9 = Mild anxiety, 10 to 14 = Moderate anxiety, and ≥15 = Severe anxiety.
- 6) The BRIEF-A is a standardized 75-item rating scale in 9 scales and 2 summary index scales that assesses aspects of executive function and problems with self-regulation from the perspective of the individual. The subject rates each item on a 3-point Likert scale (Never, Sometimes, or Often) based on their experiences within the last month. Higher scores indicate poorer executive function. The Global Executive composite (GEC) raw score is the sum the Behavioral Regulation Index (BRI) raw score and Metacognition Index (MI) raw score. The BRI raw score is the sum of raw scores of subscales Inhibit, Shift, Emotional Control, and Self-Monitor scales. To calculate the MI raw score, sum the raw scores obtained for the Initiate, Working Memory, Plan/Organize, Task Monitor; and Organization of Materials scales. Raw GEC scores, BRI, MI, and their component subscale (individual scales) will be converted to T-scores using Appendix A of the BRIEF-A Professional Manual¹⁰, and the change from baseline in T-scores will be calculated.

- 7) The Symptoms of Depression Questionnaire (SDQ) is a 44-item, self-reported depression scale, designed to measure the severity of symptoms of depression that inquires about an extensive number of depressive symptoms. The subject self-rates/scores each item on a 6-point scale (1 to 6) as it pertains to the past month. Each item is rated based on a subject's perception of what is normal for the individual (score = 2), what is better than normal (score = 1), and what is worse than normal (scores = 3 to 6). SDQ subscales are as follows: SDQ-1 subscale includes items related to lassitude, mood, and cognitive functioning; SDQ-2 subscale includes items related to anxiety, agitation, irritability, and anger; SDQ-3 subscale includes items related to suicidal ideation; SDQ-4 subscale assesses disruptions in sleep quality; and SDQ-5 subscale includes items on changes in appetite and weight.
- 8) Adult ADHD Quality of Life (AAQoL) is a 29-item questionnaire that measures how ADHD has impacted the subject's quality of life over the past 2 weeks. The AAQoL includes 4 subscales: life productivity, psychological health, relationships, and life outlook. The subject rates/scores each item on a 5-point Likert scale, where 1 = Not at all/Never, 2 = A little/Rarely, 3 = Somewhat/Sometimes, 4 = A lot/Often, and 5 = Extremely/Very often. For subscale calculations, items are transformed such that a score of 1 = 0, 2 = 25, 3 = 50, 4 = 75, and 5 = 100 and then the sum of these transformed subscale items is averaged by the number of items.

Life productivity scores come from items 1, 2, 3, 4, 5, 11, 22, 23, 24, 25 and 26 and the values are reversed, i.e., a score of 1 becomes a score of 5, a score of 2 becomes a score of 4, a score of 3 remains a 3, and so on. This is then transformed and averaged as stated above.

Psychological health scores come from items 6, 7, 8, 13, 20 and 21 and the values are reversed, i.e., a score of 1 becomes a score of 5, a score of 2 becomes a score of 4, a score of 3 remains a 3, and so on. This is then transformed and averaged as stated above.

Relationships scores come from items 9, 10, 12, 18 and 19. This is then transformed and averaged as stated above.

Life outlook scores come from items 14, 15, 16, 17, 27, 28 and 29. This is then transformed and averaged as stated above.

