## 6.1.7. Adult ADHD Quality of Life Scale (AAQoL)

The AAQoL is a self-report rating scale designed to assess health-related quality of life (HRQL) that has been validated in adult patients with ADHD (**Brod et al., 2006; Brod et al., 2015**). Development of the scale followed the industry guidance "Patient-Reported Outcome Measures: Use in Medical Product Development to Support Labeling Claims" set by the Food and Drug Administration (http://www.fda.gov/downloads/Drugs/GuidanceComplianceRegulatoryInformation/Guida nces/UCM193282.pdf). The AAQoL is a 29-item questionnaire that measures how ADHD has impacted the subject's quality of life over the past 2 weeks. The AAQoL includes 4 domains:

- 1) Life Productivity: 11 items, including "getting things done on time," "completing projects or tasks," "remembering important things," and "balancing multiple projects";
- Psychological Health: 6 items, including "feeling anxious," "overwhelmed," and "fatigued";
- 3) Relationships: 5 items, including "tension," "annoyance," and "frustration in relationships"; and
- 4) Life Outlook: 7 items, including "perceptions that energy is well spent," "people enjoy spending time with you," "you can successfully manage your life," and "you are as productive as you would like to be".

The subject rates/scores each item on a 5-point Likert scale, where 1 = Not at all/Never, 2 = A little, 3 = Somewhat, 4 = A lot, and 5 = Extremely/Very often. To derive overall and subscale scores, item scores are transformed to a 0 to 100-point scale, and higher scores indicate better HRQL. It takes approximately 5 to 10 minutes to complete the AAQoL.

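### The SAP states no reversal for the five AAQoL Relationships items, which appears to conflict with the score direction in Protocol 6.1.7; the direction of each item must be confirmed.

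*SAP*

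**What the plan says.** SAP 2.5 item 8 rates each AAQoL item from 1 (not at all or never) to 5 (extremely or very often). The mapping begins "For subscale calculations, items are transformed such that a score of 1 = 0" and rises by 25 points per category to 100 at a response of 5. A subscale is the average of its transformed items.

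Two subscales are reversed before this mapping. The SAP says of the first: "Life productivity scores come from items 1, 2, 3, 4, 5, 11, 22, 23, 24, 25 and 26 and the values are reversed". It gives the second the same treatment, again spelled out in full: "Psychological health scores come from items 6, 7, 8, 13, 20 and 21 and the values are reversed".

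The other two carry no such clause. The whole rule for the subscale at issue here is "Relationships scores come from items 9, 10, 12, 18 and 19. This is then transformed and averaged as stated above". The last of the four is handled in the same manner, likewise without any mention of reversal: "Life outlook scores come from items 14, 15, 16, 17, 27, 28 and 29. This is then transformed and averaged as stated above".

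Protocol 6.1.7 fixes the direction for overall and subscale scores alike: "item scores are transformed to a 0 to 100-point scale, and higher scores indicate better HRQL". It describes the domain in question as "Relationships: 5 items, including 'tension,' 'annoyance,' and 'frustration in relationships".

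Change from baseline in the AAQoL total and in the subscales are items 14 and 15 of the efficacy analyses in SAP 4.4. The total appears in Table 11.10 and Figure 7, and the AAQoL results in Listing 11.7.

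**The concern.** On a never-to-very-often scale, frequent tension or annoyance is a worse state. Under the SAP rule as written, the most frequent response to such an item scores 100, the best value, where Protocol 6.1.7 requires a low score. The closing phrase about transforming and averaging does not bring the reversal in. The same phrase closes the two reversed subscales, after their reversal has been set out separately.

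If some of items 9, 10, 12, 18 and 19 are negatively worded and the programs follow the SAP text, improvement on those items would be counted as worsening, and worsening as improvement. That would affect the Relationships subscale and, through it, the AAQoL total. The primary safety endpoints would not be affected.

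**Working it through.** **1. Labels against reversal**

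| Subscale | Items | Example labels in Protocol 6.1.7 | Reversed in SAP 2.5? |
|---|---|---|---|
| Life productivity | 11 | positive-sounding (timeliness, completing tasks) | yes |
| Psychological health | 6 | adverse (anxious, overwhelmed, fatigued) | yes |
| Relationships | 5 | adverse (tension, annoyance, frustration) | no |
| Life outlook | 7 | positive (energy well spent, others enjoy your company) | no |

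The item lists hold 11 + 6 + 5 + 7 = 29 items and use each of items 1 to 29 once, matching the protocol's domain counts. The question is therefore direction, not item assignment. Psychological health is the closest comparison for Relationships: it also has adverse labels, and it is reversed.

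**2. The scoring rule**

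Transformed item = 25 × (response - 1). Reversal = 6 - response. Subscale = mean of its transformed items. With all five Relationships items answered 5, the SAP rule gives 25 × 4 = 100. If all five are negative, the correct score is 0. If three are negative, it is (3 × 0 + 2 × 100)/5 = 40.

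**3. Equal change in every item (an assumption)**

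Let k be the number of negative Relationships items left unreversed, and let every item truly improve by d points. Neither document gives k, so the whole range is shown. The subscale shows [(5 - k)d - kd]/5 = d(5 - 2k)/5. The SAP gives no formula for the total, so two are assumed: the mean of 29 items, which shows (29 - 2k)/29 of the true change, and the mean of four subscales, which shows [3 + (5 - 2k)/5]/4.

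| k | Subscale, share of true change | Subscale shown for a true +25 | Total, 29-item mean | Total, mean of four subscales |
|---|---|---|---|---|
| 0 | 100% | +25 | 100% | 100% |
| 1 | 60% | +15 | 93% | 90% |
| 2 | 20% | +5 | 86% | 80% |
| 3 | -20% | -5 | 79% | 70% |
| 4 | -60% | -15 | 72% | 60% |
| 5 | -100% | -25 | 66% | 50% |

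**4. Unequal change**

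One category is 25 points on an item, so 25/5 = 5 points on the subscale.

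- k = 3; one negative and both positive items improve one category. True change 3 × 5 = +15; shown (-1 + 2) × 5 = +5. The sign is right although k is 3.
- k = 2; both negative items and one positive item improve one category. True change +15; shown (-2 + 1) × 5 = -5. The sign is wrong although k is 2.
- k = 1; only the negative item changes, and it worsens one category. True change -5; shown +5. A worsening appears as a gain.

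**5. Reversing all five without checking**

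The subscale would then show (2k - 5)/5 of an equal true change: 100% at k = 5, 60% at k = 4, 20% at k = 3, and the wrong sign at k of 2 or less. A blanket reversal is right only if all five items are negative.

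**The case against.** The strongest objection is that short labels do not prove how an item is worded. The documents show this themselves: the protocol describes a domain as "Life Productivity: 11 items, including 'getting things done on time", which sounds positive, yet the SAP reverses that subscale. Neither document prints items 9, 10, 12, 18 and 19 or ties a label to an item number. The SAP's lists divide the 29 items exactly and may have been copied from scoring instructions, in which case the rule could be right. This objection stands in full against any claim that the subscale is scored backwards. It does not remove the apparent conflict, which only an item-level check can settle.

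A reader might also infer that the subscale and total are bound to be understated, with the sign wrong once three items are negative. That holds only when all items change equally; the examples of unequal change break it in both directions.

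Nor is it right that a programmer has nothing but this rule. The SAP's reference list includes the protocol, which states the score direction and cites two AAQoL validation studies. What is true is narrower: the SAP names a manual for BRIEF-A scoring but cites no scoring source for the AAQoL. Protocol 7.1 also lets the SAP's statistical methods supersede its own, so a programmer could reasonably follow the SAP text.

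**Conclusion.** The point holds as an apparent conflict that should be resolved, with medium confidence. The absence of a stated reversal for Relationships is a fact of the SAP text. Whether it is an error depends on item wording that the documents do not give: if no item is negative, nothing is wrong. Any negative item left unreversed contributes to the subscale and the total with the wrong sign.

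The percentages illustrate equal change in every item across all possible k; they do not measure a demonstrated bias. The figures for the total rest further on an assumed formula. Two of the 15 secondary efficacy endpoints are touched. Both are descriptive, no hypothesis test depends on them, and the scores can be recomputed from the collected responses. It is worth correcting before the outputs are produced, but it is no threat to the study's main purpose.

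**What to change.** 1. Check the direction of items 9, 10, 12, 18 and 19 one by one against the instrument's scoring instructions.
2. In SAP 2.5 item 8, reverse each item confirmed negative (1 becomes 5, 2 becomes 4, and so on) before the 0-100 transformation. Leave any positive item unreversed. If none is negative, say so. Cite the scoring source.
3. Using the confirmed directions, check in the program that the best possible answers score 100 on every subscale. Under the present rule Relationships would give 100 × (5 - k)/5, that is 100, 80, 60, 40, 20 or 0 for k = 0 to 5, so any k of 1 or more would be caught. The check is only as good as the item directions fed into it.
4. Apply the corrected scoring to the AAQoL subscale summaries (SAP 4.4 item 15), Table 11.10, Figure 7 and any derived scores in Listing 11.7.

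Stating the formula for the AAQoL total in the same edit would be a useful separate clarification; its absence is not part of this error.

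The cost is a check of five items, two or three sentences in the SAP and one program check. No new data are needed.
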